4.2.2 Secondary Outcome Measures

A secondary aim of the present study is to examine the effects of exenatide on the absorption of

The Effects of Exenatide, a GLP-1 Agonist, on Alcohol Self-Administration in Heavy Drinkers
Version 1.8 10.5.20

alcohol in a sample of heavy drinkers. It is hypothesized that areas under the breath alcohol concentration curves in heavy drinkers obtained during the first 40 minutes after ingestion of the priming drink of alcohol will be significantly lower in subjects when they receive exenatide as compared to when they are given sham injections. Another secondary goal of this study will be to determine whether blood glucose levels enter into the hypoglycemic range in any of the study subjects receiving the combination of alcohol and exenatide. It is hypothesized that the proportion of subjects with post-trial blood glucose levels in the hypoglycemic range will not differ significantly between the sham injection and exenatide treatment trials.

5 Study Design

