All study procedures will be conducted at the Clinical Studies Unit at Boston Medical Center and the General Clinical Research Unit at Boston University Medical Campus. At the first screening visit a research assistant will greet the prospective subject and provide a copy of the consent form to read prior to meeting with a study physician. After reviewing the consent, candidates will meet with study physician and receive an explanation of the study purpose and requirements. If still interested after receiving an explanation of the study, the candidate will be given an opportunity to review, inquire about, and sign the study informed consent form. A consent questionnaire quiz will be administered to ensure that the subject understands the study procedures. Any incorrect answers will be reviewed until the consenting physician is satisfied that the subject comprehends the misunderstood information. Subjects' BAC will be measured immediately after signing consent to ensure that consent was given while not

The Effects of Exenatide, a GLP-1 Agonist, on Alcohol Self-Administration in Heavy Drinkers
Version 1.8 10.5.20

intoxicated. BAC must be 0.000 when signing the informed consent document. The consenting physician will document the consent process in a progress note in the subject's source binder. Subjects who are deemed to lack decisional capacity will not be enrolled in this study.

B) Protections against Risks

Risks of study medication

To minimize the risk of adverse health events we will instruct subjects to contact study staff with any questions or concerns about changes in health effects after initiating study medication/sham injection. Trained medical staff will evaluate any reported adverse effects and make a clinical determination about continuation in the trial and referral for medical care. Subjects will be given a wallet card that includes a phone number with 24/7 coverage for medical emergencies.

Because of evidence that exenatide can adversely affect fetal development in rats, women will be excluded from study entry if they have a positive urine pregnancy test or if they are of childbearing age and are either not using appropriate methods of contraception or practicing abstinence.

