Study randomization: Subjects will be randomized to a crossover sequence of drug exposure. Subjects will be assigned to one of two groups, with one group receiving exenatide in the alcohol challenge Trial #1 and the other receiving exenatide prior in the alcohol challenge Trial #2. Randomization of subjects will be accomplished using a stratified randomization procedure that will allow for between-group balance for drinking status (heavy vs. very heavy). Heavy drinking is defined as ≥ 21 and < 35 standard drinks per week for men, and ≥ 14 and < 28 standard drinks per week for women. Very heavy drinking is defined as ≥ 35 standard drinks per week for men, and ≥ 28 standard drinks per week for women. This stratified randomization will minimize the possibility that the order of study drug administration seems to influence outcomes when order effects are actually related to differences in severity of drinking between the two groups of subjects who are receiving the study medication in a different order. On the day of randomization, subjects will undergo an alcohol breath test, urine drug screening, assessment of concomitant medications, and the TLFB. Subjects who have purposefully abstained from drinking and achieved 14 days of abstinence prior to the challenge will be discontinued from participation for ethical reasons⁴⁹.

Alcohol Challenge Trials 1 & 2: Subjects will return to the laboratory within 14 days of the baseline assessment to complete the alcohol Challenge Trial #1. Prior to the visit, subjects will complete a COVID-19 symptom screening questionnaire following standard of care procedures. If the subject does not complete the screening questionnaire before arriving in clinic, study staff will administer the questionnaire outside of the clinic at a 6-foot distance. If the subject answers 'yes' to any question about known COVID symptoms, their in-clinic visit will be cancelled and they will be advised to contact their PCP and/or get tested at a testing center. Concomitant medications, urine drug screening, Blood Alcohol Concentration (BAC) will be assessed to determine eligibility to proceed with the challenge. A BAC reading of 0.000 is required at each visit to continue with the study procedures. For safety reasons, subjects will be asked to arrange transportation plans that does not include driving themselves home.

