Subjects will be given a priming drink designed to increase the subject's blood alcohol level (BAL) to 0.03g/dl, using the alcohol of their choice that is 24% Alcohol By Volume (ABV) or greater. Drinks will be mixed with a sugary mixer (3:1 Mixer:Alcohol) to preclude the occurrence of hypoglycemia. The volume of alcohol will be calculated using an online tool developed by UW-Madison (<http://dionysus.psych.wisc.edu/WebCMS/baccalc.htm>) based on a formula described by Watson⁵¹. The subjects will be asked to drink the priming drink over a period of 5 minutes. The purpose of the priming drink is to normalize drinking in the laboratory.

Absorption period. Subjects will be observed for 40 minutes following the priming dose of alcohol. This period will provide ample time for subjects to reach the target BAC. Breathalyzer readings will be completed at 10 minutes intervals.

Alcohol self-administration Blocks 1 and 2. In each of the alcohol self-administration Blocks, subjects will be presented with four drinks, each mixed to raise their BAC by 0.0125g/dl. They will be told that they can either consume the desired number of drinks over the following 60 minutes, or they will receive the equivalent dollar amount of the cost of each drink (\$3.00) they did not consume. At the end of each 1-hour session the drinks will be removed and the volume of alcohol remaining will be measured with a graduated cylinder. Cravings will be assessed using the AUQ and VAS every 30 min during the self-administration blocks. BAC levels will be obtained at the end of the Block 2 session as will blood glucose levels. Blood glucose levels will be measured at the end of Block 2 using a glucometer and blood obtained from a pinprick sample. If the subject is found to be hypoglycemic (glucose < 70 mg/dL), staff will give the subject orange juice and re-test in 30 minutes. If the subject is found to be hyperglycemic (glucose > 300 mg/dl), staff will escort the subject to the BMC emergency department for evaluation. At the end of this session subjects will also be asked to rate their experience of nausea using a visual analog scale developed to assess nausea in an emergency department⁵². Subjects will be assessed for safety prior to subjects leaving the laboratory. Subjects will not be released until their BAC is below 0.04 g/dl and they are not behaviorally impaired.

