2. Subjects will report lower levels of craving as measured by the Visual Analog Scale (VAS) and the Alcohol Urge questionnaire (AUQ) during the exenatide Challenge Trial compared to the sham injection Challenge Trial.	Craving measures (AUQ and VAS) collected at 30-minute intervals during the self-administration trials will be used to test the effect of exenatide on alcohol craving. A mixed models approach will be used to test for differences in craving between the exenatide and sham injection Challenge Trials. Within-subject factors for this analysis will include Treatment and Time Block. Trial order will be used as covariate in these analyses to allow evaluation as to whether the order of treatments has a significant effect on the outcome.
Hypothesis 3: Areas under the breath alcohol concentration curves (AUC's) in heavy drinkers obtained during the first 40 minutes after ingestion of the priming drink of alcohol will be significantly lower in subjects when they receive exenatide as compared to when they are given sham injections	AUC's for BAC obtained using data obtained during the 40-minute absorption period will be compared between Challenge Trials using a repeated measures mixed models approach. In addition, individual BAC values obtained at 10-minute intervals after alcohol ingestion of the priming drink also will be compared between the sham injection and exenatide treatment trials using a repeated measures mixed models approach. A significant time x trial interaction value also will be taken to indicate a significant between trial difference in the rates of alcohol absorption.
Hypothesis 4. The proportion of subjects with post-trial blood glucose levels in the hypoglycemic range will not differ significantly between the sham injection and exenatide trials.	The proportion of subjects with blood glucose values below 50 mg/dl will be compared within subjects using the McNemar's test. We hypothesize that there will be no difference in blood glucose levels between the alcohol Challenge Trials.

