12.2 Sample Size Determination

A group size of 28 completers was selected for use in this study based on an assumed effect size of 0.7 suggested by similar alcohol self-administration studies with amount consumed as the primary outcome^{42,44}. This effect size is in the range we found for the anticonvulsant zonisamide used in a similar alcohol self-administration study⁴³. The sample size for this study is based on an estimated reduction of 1.5 standard drinks with an estimated standard deviation (2.1) of the between Challenge Trial differences in alcohol self-administration, with an effect size

The Effects of Exenatide, a GLP-1 Agonist, on Alcohol Self-Administration in Heavy Drinkers
Version 1.8 10.5.20

of this magnitude (i.e. 0.7). This requires a sample size of 28 to allow for detection of a significant within-subject difference in alcohol consumption with an alpha value of 0.01 and power value of 0.81. Based on an estimated 15-20% rate of non-completion for randomized subjects, we anticipate randomizing 36 subjects to achieve a sample of 28 completers. Given our experience with recruiting AUD populations into clinical trials, we expect a screening exclusion rate of roughly 50%. Approximately 72 subjects will be consented and screened in clinic to yield a sample of 36 eligible subjects.

Given that this a laboratory based experiment we do not plan to conduct any planned interim analyses in this study.

13 Ethics/Protection of Human Subjects

This study is to be conducted according to applicable US federal regulations and institutional policies (which are based in federal regulations, guidance, and ICH Good Clinical Practice guidelines).

This protocol and any amendments will be submitted to the Boston Medical Center and Boston University Medical Campus IRB, for formal approval of the study conduct. The decision of the IRB concerning the conduct of the study will be made in writing to the investigator. A copy of the initial IRB approval letter will be provided to the sponsor before commencement of this study.

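### The only planned hypoglycemia analysis uses complete pairs, so a measured glucose value after exenatide in Trial 1 is left out if the subject has no Trial 2

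*Combined protocol and SAP*

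**What the plan says.** Section 4.2.2 sets a secondary goal for glucose: to "determine whether blood glucose levels enter into the hypoglycemic range in any of the study subjects receiving the combination of alcohol and exenatide". That covers every exenatide exposure and does not call for a sham partner.

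Section 12.1 turns this into Hypothesis 4, which is worded as no difference: "The proportion of subjects with post-trial blood glucose levels in the hypoglycemic range will not differ significantly between the sham injection and exenatide trials". The analysis given for it is: "The proportion of subjects with blood glucose values below 50 mg/dl will be compared within subjects using the McNemar's test". No analysis set, rule for subjects with a single trial, or tabulation by treatment accompanies it. Hypotheses 1 to 3 in the same table use mixed models.

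On the data, Section 9 states: "Blood glucose levels will be measured at the end of Block 2 using a glucometer and blood obtained from a pinprick sample". The two sequences are described there "with one group receiving exenatide in the alcohol challenge Trial #1 and the other receiving exenatide prior in the alcohol challenge Trial #2".

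On losses, Section 12.2 plans 36 randomized and 28 completers: "Based on an estimated 15-20% rate of non-completion for randomized subjects".

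On leaving the study, Section 6.1 (Protections against Risks, study medication) says that medical staff will evaluate reported adverse effects and "make a clinical determination about continuation in the trial and referral for medical care". Under the risks of alcohol self-administration, the same section lets staff halt participation for emergent safety issues and reminds subjects that they may stop at any time.

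For a low reading itself, Section 9 states: "If the subject is found to be hypoglycemic (glucose < 70 mg/dL), staff will give the subject orange juice and re-test in 30 minutes".

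**The concern.** The stated question and the stated test cover different subjects. An exenatide-first subject who finishes Trial 1 has a valid post-exenatide glucose value. If that subject has no Trial 2, the value answers the Section 4.2.2 question but forms no pair, so McNemar's test cannot use it. The mixed models planned for Hypotheses 1 to 3 can keep a subject with one trial, so the method chosen for the glucose question is the one that cannot.

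The stake is the credibility of a safety statement. Section 6.1 itself says that the combined effect of GLP-1 agonists and alcohol on glucose is not adequately studied in humans. If subjects with a low value are less likely to return, the analysis describes those who tolerated Trial 1 well enough to come back. The test also has little ability to reject with so few subjects, so a non-significant result would come easily and would match the stated hypothesis.

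**Working it through.** **1. The plan's own figures.**
- Section 12.2 bases n = 28 on the alcohol outcome. A paired t-test with effect size 0.7 and two-sided alpha 0.01 gives power 0.815 at n = 28, which reproduces the stated 0.81. No size or power is given for the glucose test.
- Going from 36 to 28 is 8/36 = 22.2% non-completion. At the stated 15–20%, 36 × 0.15 = 5.4 and 36 × 0.20 = 7.2 subjects are lost. Conversely, 28/(1 − 0.20) = 35, close to the stated 36.

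**2. Exenatide exposures without a pair.** Assumptions: sequences balanced 18:18, all losses after a full Trial 1 with glucose measured. Half of those lost are then exenatide-first.

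| Non-completers | Pairs | Unpaired exenatide values | All exenatide values | Share left out |
|---|---|---|---|---|
| 5.4 (15%) | 30.6 | 2.7 | 33.3 | 8% |
| 7.2 (20%) | 28.8 | 3.6 | 32.4 | 11% |
| 8 (36 to 28) | 28 | 4 | 32 | 12.5% |

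With 28 pairs, the total could be anywhere from 28 to 36, depending on how many of the 8 were exenatide-first. Sessions stopped before the end of Block 2 have no scheduled value and would lower these counts.

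**3. Cost if leaving is unrelated to glucose.** With zero events the exact two-sided 95% upper bound is 1 − 0.025^(1/n):
- n = 28: 12.3%
- n = 32: 10.9%

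**4. Cost if a low value makes leaving more likely.** The documents give no event rate and no rate of leaving after an event, so both are assumed. Let p be the exenatide event rate, q the chance of leaving after a Trial 1 event, and 20% the loss otherwise. Assume no sham events.

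Expected paired exenatide events = 18p(1 − q) + 18 × 0.8p.

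Expected pairs = 18[p(1 − q) + 0.8(1 − p)] + 18 × 0.8.

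| True p | q = 20% | q = 50% | q = 100% |
|---|---|---|---|
| 1% | 1.0% | 0.8% | 0.5% |
| 5% | 5.0% | 4.1% | 2.6% |
| 10% | 10.0% | 8.3% | 5.3% |

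Example, p = 5% and q = 100%: events 0 + 0.72 = 0.72; pairs 13.68 + 14.4 = 28.08; ratio 2.6%. In that extreme case the chance that at least one exenatide event is observed and every one is dropped is (1 − 0.95^18) × (1 − 0.8 × 0.05)^18 = 0.603 × 0.480 = 29%.

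**5. What a few events mean.** If all discordant pairs point to exenatide, the exact two-sided McNemar p-value is 2 × 0.5^m for m such pairs. Five give 0.0625, six give 0.031, and eight give 0.0078. A single low value in an unpaired exenatide-first subject would read as 0/28 in the paired analysis and 1/32 = 3.1% over all exposures. Four would read as 0/28 against 4/32 = 12.5% (exact 95% interval 3.5% to 29.0%).

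**The case against.** A reader might infer that such an event goes uncounted altogether. The documents do not support that. The Section 10.1 definition of an adverse event includes abnormal laboratory findings, Section 10.2 collects adverse events until the end of participation, Section 10.3 summarizes them for the IRB, and Section 11.3 lists a blood glucose form. The event would leave the hypothesis test, not the study record. What remains is that none of these sections plans a tabulation by treatment with a denominator.

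A reader might also infer that hypoglycemia leads to discontinuation. No section says so. The stated response is juice and a re-test, and Section 10.4 has no glucose criterion. Sections 9 and 6.1 add a sugary mixer as a precaution, diabetic subjects are excluded, and Section 6.1 reports no increase in hypoglycemia with GLP-1 in fasting healthy subjects. Event rates of 5–10% below 50 mg/dl have no documentary basis, and q = 100% is the end of the range.

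Nor must the treatment comparison lean toward no difference. Both trials involve alcohol, and a sham-first subject with a low value who leaves is dropped in the same way. With equal event rates and equal leaving after an event, the losses cancel in the comparison. They do not cancel in the exenatide rate itself, which is what Section 4.2.2 asks about. Likewise, a Trial 2 exenatide value usually has a sham partner but not always, since a Trial 1 glucose value can be missing.

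Finally, the exclusion of unpaired values follows from how McNemar's test works. Section 12.1 does not write a completers-only rule, and reporting proportions over everyone measured would not contradict it. That is fair, but the section does not plan that report either.

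**Conclusion.** The mismatch holds without any assumption: the goal covers any exenatide exposure, and the only planned analysis covers complete pairs. Its size is modest. On the plan's figures about 3 to 4 of about 32 exenatide exposures could be left out, given balanced sequences and losses after a completed Trial 1. If leaving is unrelated to glucose, the loss is precision only, 12.3% against 10.9% for the zero-event bound. If a low value makes leaving more likely, the exenatide rate is understated. The documents allow that route but do not state it, and they give nothing from which its size can be fixed, so the table of assumed rates shows a range and is not an estimate.

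This is worth changing because the better summary uses data already collected. It is not evidence that the protocol hides hypoglycemia.

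**What to change.** In Hypothesis 4 of Section 12.1:

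- Make the main result the number and proportion of subjects with post-trial glucose below the analysis threshold, among all subjects with a glucose value after an exenatide session, with an exact 95% confidence interval. Give the same for all sham sessions, whether or not the other trial was completed.
- Keep McNemar's test as the supporting comparison and state that it uses complete pairs.
- List by treatment any low value in a subject without a second trial.
- Reconcile the two definitions so that the table uses one stated analysis threshold. Section 9 calls a value below 70 mg/dL hypoglycemic, and Section 12.1 analyzes values below 50 mg/dl.

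The cost is a few sentences and one table, with no added subjects or procedures. The small downside is that the all-exposure proportions are not fully paired, which is why the paired test stays. The change does not recover a value for a session stopped before the end of Block 2, so the number of such sessions should be shown beside the denominators.

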11.3 Case Report Forms

The study case report form (CRF) will be the primary data collection instrument for the study. All data requested on the CRF will be recorded. All missing data will be explained. If a space on the CRF is left blank because the procedure was not done or the question was not asked, a written explanation will be included to detail why the data was not recorded. If the item is not applicable to the individual case, a notation will be made. All entries on will be printed legibly in black ink.

The Effects of Exenatide, a GLP-1 Agonist, on Alcohol Self-Administration in Heavy Drinkers
Version 1.8 10.5.20

If any entry error has been made, to correct such an error, a single straight line will be drawn through the incorrect entry and the correct data will be entered closely to the original data. All such changes will be initialed and dated. There will be no erasures or white-out on CRFs. For clarification of illegible or uncertain entries, the clarification will be printed near the item, then initialed and dated. Electronic CRFs in the REDcap system will include an audit trail.

The CRFs that will be used in this study are:

Demographics
Concomitant Medications
Adverse Events
Birth Control Assessment
Urine Drug Screening
Vital Signs
Blood Alcohol Level
Laboratory summary sheet
Time-line Follow-back
Pregnancy test
Birth control assessment
Medical History
Blood Glucose
Nausea VAS
Physical Examination
MINI diagnoses summary
Medication Compliance log
Eligibility
ECG
C-SSRS
CIWA-AR
OCDS
AUQ
VAS

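### Hypothesis 4 also predicts no difference in glucose levels, but no analysis compares levels, and a non-significant McNemar test on values below 50 mg/dl cannot support that prediction

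*Combined protocol and SAP*

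**What the plan says.** Section 4.2.2 makes glucose a secondary outcome. It hypothesizes that the "proportion of subjects with post-trial blood glucose levels in the hypoglycemic range will not differ significantly" between the sham and exenatide trials. The left column of Hypothesis 4 in section 12.1 repeats this.

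The analysis column then says two things. The first is the test: "The proportion of subjects with blood glucose values below 50 mg/dl will be compared within subjects using the McNemar's test". The second is a further hypothesis: "We hypothesize that there will be no difference in blood glucose levels between the alcohol Challenge Trials". No mean, paired difference, model or confidence interval for glucose appears anywhere in section 12.

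The numerical data will exist. Section 9 (Alcohol self-administration Blocks 1 and 2) states: "Blood glucose levels will be measured at the end of Block 2 using a glucometer". The list of forms in section 11.3 includes "Blood Glucose". The same part of section 9 sets a different threshold from the one analysed: "If the subject is found to be hypoglycemic (glucose < 70 mg/dL". Section 12.2 plans for 28 completers and gives no power, margin or precision target for Hypothesis 4.

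**The concern.** The added sentence is about levels, and the test is about crossing a low threshold. Levels can shift by a clinically interesting amount while few or no subjects pass below 50 mg/dl. The test would then be non-significant, and the sentence invites the reader to take that as confirmation that levels did not differ. Because the hypothesis predicts no difference, low power works in favour of the prediction.

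Section 6.1 itself says that the joint effect of GLP-1 agonists and alcohol on blood glucose has not been adequately studied in humans. This trial will hold a paired reading in mg/dL for each completer, and the planned comparison reduces each pair to two yes/no values. Hypotheses 1 to 3 all receive mixed models on continuous data.

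**Working it through.** **Inputs from the documents.** 28 completers, effect size 0.7 (a 1.5-drink reduction over an SD of 2.1), alpha 0.01 and power 0.81 (section 12.2); the 50 mg/dl cut-off (section 12.1); one glucometer reading per trial (section 9). The documents give no glucose mean, SD, within-subject correlation or expected change, so every such value below is an assumption.

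**The plan's own figure.** A paired t-test, two-sided alpha 0.01, effect size 0.7, n = 28, gives power 0.815 from the noncentral t. With 1.5/2.1 = 0.714 it is 0.834. The stated 28 and 0.81 reproduce. They concern alcohol consumed, not glucose.

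**What McNemar needs.** If all k discordant subjects go one way, the exact two-sided p-value is 2 × 0.5^k.
- k = 5: 2 × 0.03125 = 0.0625
- k = 6: 2 × 0.015625 = 0.031
- k = 8: 2 × 0.0039 = 0.0078

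So at least 6 are needed at 0.05, and 8 at 0.01. The plan does not say which form of the test it means. The continuity-corrected version also needs 6 (p = 0.041). The uncorrected chi-square version needs 4 (p = 0.0455).

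**Power of the planned test.** Suppose a fraction π of subjects fall below 50 mg/dl on exenatide only and none on sham only. Power at two-sided 0.05 is then P(X ≥ 6) with X binomial(28, π).

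| π | Expected discordant (28π) | Power, exact |
|---|---|---|
| 5% | 1.4 | 0.2% |
| 10% | 2.8 | 5.5% |
| 15% | 4.2 | 23.5% |
| 20% | 5.6 | 50% |

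This table needs no assumption about the glucose distribution. With the uncorrected version, P(X ≥ 4) is 30.5% at π = 10%, which is still low.

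**Zero events.** The two-sided 95% upper limit for 0 of 28 is 1 − 0.025^(1/28) = 12.3%.

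**What the same readings give as numbers.** The 95% CI half-width for a paired mean difference is t(0.975, 27) × SD/√28 = 2.052 × SD/5.292.
- SD of differences 15: 5.8 mg/dl
- SD 20: 7.8 mg/dl
- SD 30: 11.6 mg/dl

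At two-sided 0.05, 80% power is reached for a mean difference of 0.55 SD, that is 8.2, 11.0 and 16.5 mg/dl.

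**Illustration, all inputs assumed.** Take normal glucose, sham mean 100, SD 20, correlation 0.5, and a true fall of 15 mg/dl on exenatide. The proportion below 50 is Φ(−2.5) = 0.6% on sham and Φ(−1.75) = 4.0% on exenatide, or 28 × 0.040 = 1.1 subjects. McNemar power is about 0.05%. The SD of differences is 20 × √(2 × 0.5) = 20, so the standardized difference is 15/20 = 0.75 and paired-t power is 97%. Over four scenarios (mean 90 to 110, SD 15 to 25, fall 15 to 20), McNemar power was 0.05% to 0.7% and paired-t power 97% to 99.9%.

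**The case against.** The strongest reply is that the formal hypothesis and the test agree. Section 4.2.2 asks whether any subject enters the hypoglycemic range, and a within-subject comparison of threshold counts answers that. The sentence on levels may be loose shorthand for levels in the hypoglycemic range. This stands as far as it goes: the mismatch lies in one added sentence, and it would be wrong to infer that Hypothesis 4 as a whole has the wrong test. But the sentence is in the plan, it is worded as a hypothesis, and nothing tests it.

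A second reply is that the readings are not ignored. They go on a form and trigger action below 70 and above 300 mg/dL. That is also right: they are missing only from the statistical comparison.

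A third is that the scarcity of events comes partly from the 50 mg/dl cut-off. In the illustration above, 6.7% (sham) and 22.7% (exenatide) would be below 70, with McNemar power of 26%. This is fair, and it is a further reason to reconcile the two thresholds. It still does not make a count into a test of levels.

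A reader might also infer that the comparison is spoiled because sugar comes in the drinks ("Drinks will be mixed with a sugary mixer (3:1 Mixer:Alcohol) to preclude the occurrence of hypoglycemia") and less drinking is expected on exenatide, so that recorded sugar intake goes unused. The documents do not support that. Sugar is not recorded. What section 9 provides is that "the volume of alcohol remaining will be measured with a graduated cylinder". Section 6.1 lets the mixer vary (juice or soda, for example), no listed form is named for mixer type, and the 3:1 ratio is stated under the priming dose. If exenatide reduces drinking, the resulting change in glucose is part of its total effect, so unequal loads do not bias the randomized comparison. Adjusting for consumption would condition on a post-treatment variable.

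**Conclusion.** The point holds in a limited form. The proportion hypothesis has a matching test; the levels hypothesis has none. The McNemar result cannot stand in for it: at least 6 one-directional discordant subjects out of 28 are needed, power is 0.2% to 50% when 5% to 20% fall below 50 mg/dl on exenatide only, and zero events is compatible with a true rate of up to 12.3%. Those figures rest only on 28 pairs, the exact test, two-sided 0.05 and no sham-only events. The comparison with a paired analysis, and the CI half-widths of 5.8 to 11.6 mg/dl, rest on assumed glucose values. The gap in power is wide in every scenario tried, but its exact size is not known from the documents.

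This is a secondary outcome. Neither the stopping rules in section 10.4 nor the sample size in section 12.2 depends on it. The risk is one of interpretation: an uninformative test being reported as evidence that glucose levels did not differ.

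**What to change.** In section 12.1, Hypothesis 4:

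1. Add a mixed model on the end-of-Block-2 glucose in mg/dL, with treatment and period as fixed effects and subject as the repeated unit. Report the mean exenatide-minus-sham difference with its 95% CI.
2. State that any conclusion about levels will rest on that interval and not on a non-significant McNemar test. If the team wants to claim no difference, and not only to report an estimate, it must also say in advance how small a difference would count; the plan gives no margin.
3. Report the below-threshold counts by treatment as safety data.
4. Reconcile the 50 mg/dl used in section 12.1 with the <70 mg/dL definition of hypoglycemic in section 9.
5. At most, tabulate volume consumed beside glucose as description, without adjusting the main estimate for it.

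The cost is a small amount of extra analysis on a secondary outcome. No new measurement, visit or subject is needed.
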